For dactylitis-free state at Week 16, dactylitis resolution data of the FUTURE 5 study (Mease et al, 2018) at Week 16 were used to estimate the BKZ 160mg Q4W treatment and placebo groups. The treatment effect estimate from the secukinumab 150mg treatment group at Week 16 of 56% (n=103) is assumed versus a placebo group estimate of 32% (n=124). With those assumptions and having 11% of subjects with Baseline dactylitis, the pooled PA0010/PA0011 studies have a 66% power to detect a true treatment difference of 24% (OR= 2.71).

For enthesis-free state at Week 16, enthesis resolution data from the FUTURE 5 study at Week 16 were used to estimate the BKZ 160mg Q4W treatment and placebo groups. In FUTURE 5 The treatment effect estimate from the secukinumab 150mg treatment group at Week 16 was 55% (n=141) and the placebo group estimate was 36% (n=192). Assuming a BKZ response of 55% and a placebo rate of 39% and having 25% of subjects with Baseline enthesis the pooled PA0010/PA0011 the studies have a 69% power to detect a true treatment difference of 16% (odds ratio 1.91). Treatment difference in change from Baseline in vdHmTSS at Week 16 in the overall population is estimated using the data from the FUTURE 5 study in a mixed TNF α exposure population. The BKZ 160mg Q4W group treatment difference compared to placebo is estimated to be the same as the difference in change from Baseline in vdHmTSS at Week 16 between the secukinumab 150mg group and placebo which is 0.42, assuming a SD of 1.13 for BKZ and SD=2.44 for placebo. With these assumptions the study has 76% power to detect a treatment difference of 0.42 in the planned sample size.

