4 STATISTICAL/ANALYTICAL ISSUES

4.1 Adjustments for covariates

The primary efficacy analysis will investigate the treatment effect, adjusting on the 2 randomization stratification variables:

- Region:
 - North America, Western Europe, Eastern Europe, Asia
 - or
 - North America, Eastern Europe, Western Europe + Asia if the percentage of randomized subjects is < 10% in either of the Asia or Western Europe regions
- Bone erosion (0, ≥ 1) at Baseline.

When adjusting on these 2 variables, a statistical model might not converge (ie: the likelihood maximization algorithm fails to converge). In that case, the statistical model will be run after dropping successively region and bone erosion at Baseline.

If a subject is stratified in the incorrect stratum (ie: the stratum recorded in the Interactive voice or web Response System differs from the actual stratum the subject belongs to), the actual stratum will be used for the analysis.

The secondary analyses will be adjusted on the same categorical factors as retained for the primary analysis. For continuous variables, Baseline value (of the variable of interest) will be also included as covariate where appropriate.

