8.1.2 Primary analysis of the primary efficacy variable

The primary efficacy variable will be analyzed for all subjects in the RS.

The primary endpoint is the ACR50 response at Week 16. The primary efficacy analysis will evaluate the composite estimand in the RS. The composite estimand combines the clinically meaningful improvement from Baseline in ACR50 response and not discontinuing study treatment early.

The following 4 attributes describe the estimand that will be used to define the treatment effect of interest for the primary efficacy analysis:

- Population = Subjects enrolled according to the protocol-specified inclusion/exclusion criteria and randomized to IMP.
- Subject-level outcome = ACR50 at Week 16.
- IE handling = An IE is defined as discontinuation of study treatment prior to Week 16. A composite strategy will be implemented in which a positive clinical outcome is defined as achieving ACR50 at Week 16 and not discontinuing study treatment through Week 16.
- Population-level summary measure = Conditional OR comparing BKZ to placebo.

Missing data at Week 16 that are not preceded by an IE, and any data after an IE will be imputed as non-responders. This results in a more traditional NRI approach and will be labeled as such throughout the SAP.

The statistical hypothesis for the ACR50 response at Week 16 is that the conditional OR for ACR50 response in the BKZ treatment compared to placebo treatment is equal to 1.

A logistic regression model will be used to assess the treatment effect on ACR50 response at Week 16. The model will include a fixed effect for treatment. The suitability of including randomization stratification variables (bone erosion at Baseline and region) will be assessed using Pearson and Deviance and The Hosmer-Lemeshow Goodness-of-Fit Tests (Hosmer and Lemeshow, 2000).

In the context of the Week 24 analysis, actual bone erosion at Baseline as a covariate will be based on data from the first set of reads. For Week 52 analysis, data from the second set of reads will be used.

P-values below 0.05 would lead to a reconsideration of the model to be used and if the logistic regression model is unable to converge the stratification variables will be dropped ([Section 4.1](#)). In that case, all supportive analyses as well as imputation models conducted for the primary endpoint will disregard these factors from their models.

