- If the total score is missing at a post-Baseline visit (ie, only "N" or "S" is recorded for all joints) or if JSON or ES score is missing then the missing total score will be imputed using MI imputation.

For the change from Baseline analyses, subjects who withdraw early and have radiographs taken at their early withdrawal visit should be included in the analysis. In such cases, one or more imputation methods may be applied for the subjects with less than 2 radiographs. In addition to any such imputation approach that is selected, an analysis excluding subjects with less than 2 radiographs from the analysis should be performed.

In the testing hierarchy (Table 4-5), 2 endpoints are defined based on the vdHmTSS:

- Change at Week 16 from Baseline in vdHmTSS for subjects with elevated hs-CRP and/or with at least one bone erosion at Baseline (planned to be approximately 45% of the overall population). This is the 6th endpoint in the sequential testing hierarchy.
- Change at Week 16 from Baseline in vdHmTSS for all subjects. This is the 9th endpoint in the sequential testing hierarchy.

The 2 endpoints will be analyzed in the radiographic set.

At Week 16, imaging data collected outside ± 14 days of the expected visit date will be excluded from the analysis.

For the Week 24 interim analysis only, in the primary analysis of these 2 endpoints, missing data at Week 16 will be imputed based on value at Screening (as there is no value collected in between) using MI-MCMC / Monotone regression. Since VdHmTSS is only collected at Baseline prior to Week 16, only the second MI step to address monotone missing pattern and generating 100 imputations will be processed (Section 4.2.2.2).

8.2.1.6 Enthesitis-free state at Week 16 in the subgroup of subjects with enthesitis at Baseline

The Leeds Enthesitis Index (LEI) consists of 6 items, 3 for the right part and 3 for the left part of the body. The body parts are Lateral epicondyles of the humerus, Medial femoral condyle, and

Achilles tendons. Each item is scored for tenderness with either 1 or 0 (tenderness, no tenderness, respectively). The total score ranges from 0 (no enthesitis) to 6 (severe enthesitis).

Note that LEI is collected for all subjects regardless of their Baseline score.

In case 4 items are missing, the LEI will be set to missing. If at least 3 items are available, the available items will be assessed and scored and then weighted by the number of the assessed items (AI) as shown in the formula below:

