- If a digit is recorded as affected and the circumference of the contralateral digit is missing, the normative value will be used for comparison with the affected digit.
- If a digit is selected but recorded as 'not affected' but has circumference and contralateral circumferences collected, a missing tenderness score will be considered as 1.
- If the investigator did not complete the LDI questionnaire at Baseline, it will be assumed that no digits were affected (ie, a LDI score of 0 will be assigned).

Dactylitis-free state is based on a Leeds Dactylitis Index (LDI) at Week 16 of 0, for subjects with dactylitis at Baseline ($LDI>0$).

Dactylitis-free state at Week 16 (pooled between PA0010 and PA0011) is the 8th endpoint in the sequential testing hierarchy (Table 4–5) and will be based on pooled data from PA0010 and PA0011 (for subjects in the BKZ160mg Q4W and the Placebo groups). The analysis will also be repeated using PA0010 data alone and the p-value will only be considered nominal.

A tender dactylitis count will be calculated as the sum of the tenderness scores for all digits and will be used for the PASDAS score calculation (Section 8.3.1.6).

8.2.1.8 Psoriasis Area Severity index 90 (PASI90) at Week 4 (in subjects with PSO involving at least 3% of BSA at Baseline)

This variable will be derived as described in Section 8.2.1.2.

8.2.1.9 ACR20 and ACR70 response at Week 16

The ACR20 and ACR70 responses are defined based on respectively 20% and 70% or greater improvement from Baseline in the same measures than the primary endpoint (Section 8.1.1).

8.2.1.10 Proportion of subjects with an Investigator Global Assessment (IGA) score of 0 (clear) or 1 (almost clear) AND at least a 2-grade reduction from Baseline at Week 4 and Week 16 in the subset of subjects with psoriatic skin lesions at Baseline

A static IGA for PSO will be used to assess disease severity in all subjects during the study. The Investigator will assess the overall severity of PSO using the following 5-point scale presented in [Table 8-4](#).

Table 8-4: Five-point IGA

Score	Short Descriptor	Detailed Descriptor
0	Clear	No signs of PSO; post-inflammatory hyperpigmentation may be present
1	Almost Clear	No thickening; normal to pink coloration; no to minimal focal scaling
2	Mild	Just detectable to mild thickening; pink to light red coloration; predominantly fine scaling
3	Moderate	Clearly distinguishable to moderate thickening; dull to bright red, moderate scaling

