8.2.2 Primary analysis of secondary efficacy variables

The secondary efficacy variables will be analyzed for all subjects in the RS by treatment group (except for vdHmTSS for which the analysis will be performed on the RAS).

As indicated in [Table 4–5](#), there are 8 secondary endpoints included in the testing hierarchy that will be tested in a chronological order until one is failed to be statistically significant.

For the other secondary endpoints (secondary endpoints which are not part of the testing hierarchy), the p-values produced by the statistical models will be considered nominal since these endpoints are not controlled for multiplicity.

For the secondary composite and non-composite binary endpoints, the same estimand structure (composite estimand) as the one defined for the primary efficacy analysis of the primary efficacy endpoint ([Section 8.1.2](#)) will be used. The NRI approach for handling missing data and the same analysis model will be considered, and the analysis results will be presented similarly, with the exceptions that the analyses performed on pooled data from PA0010 and PA0011 subjects will consider the region and the study-id factor as possible covariates for the modelling.

The statistical hypothesis for the binary variables at Week 16 is that the conditional odds ratio in the BKZ group compared with placebo treatment group is equal to 1.

For the secondary continuous endpoints, the analysis will evaluate the hypothetical estimand as defined below:

- Population = Subjects enrolled according to the protocol-specified inclusion/exclusion criteria and randomized to IMP.
- Subject level outcome = variable as stated in [Section 2.2.1.2](#)
- IE handling = An IE is defined as discontinuation of study treatment prior to Week 16. A hypothetical strategy for addressing IE will be implemented. This estimand targets the treatment difference in a scenario where withdrawal from study treatment does not occur, such that outcomes for subjects without an IE are as observed, and outcomes for subjects with an IE are treated as though they had completed treatment through Week 16 but on Placebo. A MI strategy will be used to impute any missing data and observed data after IE which will be set to missing prior to running MI. Such data will be imputed using reference-based MI, in which the MI model is based on data from the Placebo group.

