8.2.3 Supportive analyses of the secondary efficacy variables

As mentioned in [Table 4–2](#), the supportive analyses for all secondary variables will be performed using the modified composite estimand for binary variables (using MI-MCMC/monotone regression as in [Section 8.1.4.3](#)), the hypothetical estimand for continuous variables (using MI-MCMC/monotone regression as in [Section 8.1.4.4](#)) and OC.

For PASI90, the MI will be run on the PASI score on subjects involving at least 3% of BSA at Baseline.

For the MDA (and VLDA) MI analysis, subjects with BSA <3 at Baseline will always meet the criteria PASI ≤ 1 or BSA ≤ 3 except in the cases where a BSA score ≥ 3 is observed. Subjects involving at least 3% of BSA at Baseline will have their BSA values imputed using MI when deriving MDA (VLDA).

For enthesitis and dactylitis free-state based on the pooled data of PA0010 and PA0011 subjects (in the BKZ160mg Q4W and the Placebo group), the MI will be performed on the pooled dataset (using data from Baseline, Week 4, 8, 12 and 16) the same way as described in [Section 4.2.2.2](#):

- with the following covariates in that order for each SAS® PROC MI: region (North America, Western Europe and Eastern Europe) and study-id (“1” for PA0011 and “0” for PA0010)
- For MI on LDI : on subjects with LDI>0 at Baseline
- For MI on LEI : on all subjects (but the results will be reported for subjects with LEI>0 at Baseline).

In addition, subgroup analyses will be performed on the PASI90 response at Week 16 (in subjects with PSO involving at least 3% of BSA at Baseline) (Refer to [Section 4.8](#) for the list of subgroups of interest). The same analysis method used for the subgroup analysis of the primary endpoint will be performed, and the results will be presented similarly.

Enthesitis and dactylitis free state will be analyzed as supportive analyses in the PA0010 data only (successively using the NRI, the modified composite estimand and the OC strategies).

To assess the impact of the COVID-19 pandemic, the analysis of secondary efficacy endpoints included in the hierarchy will be repeated on the COVID-19-Free Set (on subjects from the Radiographic Set included in the COVID-19-Free-Set for the analysis of VdHmTSS) using the primary analysis method.

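### The pooled tests H7 (enthesitis-free) and H8 (dactylitis-free) leave the Baseline LEI and LDI out of the model, giving up some precision in the two lowest-powered steps ahead of H9

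*SAP*

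**What the plan says.** SAP Section 8.2.2 gives the binary secondary endpoints the primary ACR50 logistic model. Section 8.1.2 says of that model: "The model will include a fixed effect for treatment". The randomisation strata are added subject to a suitability check. For the pooled PA0010/PA0011 analyses, Section 8.2.2 "will consider the region and the study-id factor as possible covariates for the modelling". The only rule that brings in a Baseline score is in Section 4.1: "For continuous variables, Baseline value (of the variable of interest) will be also included as covariate where appropriate". H7 and H8 are binary, so it does not reach them.

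Both scores are available. On the LEI, Section 8.2.1.6 says: "Note that LEI is collected for all subjects regardless of their Baseline score", and H7 is restricted to a Baseline LEI above 0. On H8, Section 8.2.1.7 says: "Dactylitis-free state is based on a Leeds Dactylitis Index (LDI) at Week 16 of 0", among subjects with a Baseline LDI above 0. The Baseline scores are used in the supportive imputation, where Section 8.2.3 says "the MI will be performed on the pooled dataset (using data from Baseline, Week 4, 8, 12 and 16". They are not used in the confirmatory model.

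Section 2.4.2 states "69% power to detect a true treatment difference of 16" percentage points for H7 and "66% power to detect a true treatment difference of 24" points for H8. Section 4.5 tests in fixed sequence, so H7 gates H8 and both gate H9.

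**The concern.** Enthesitis-free and dactylitis-free are absolute states. A subject who enters with LEI 1 is one site from success, and a subject who enters with LEI 6 is six sites away. ACR50 and PASI90 are scaled to the subject's own Baseline, so they do not raise the question in the same way. MDA (H5) is also an absolute state, but its stated power is above 99% and little depends on precision there.

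The starting score is thus a natural candidate to explain outcome variation in H7 and H8, and it costs nothing to use. These two tests have the least power to spare. PA0010 randomisation is stratified by region and bone erosion, not by enthesitis or dactylitis severity, so neither the design nor the model balances the starting score in these subgroups. A failure for lack of precision at H7 or H8 also closes the later confirmatory claims, including the overall radiographic comparison H9.

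**Working it through.** **1. Inputs from the SAP.** H7: 55% vs 39%, 25% of subjects with Baseline enthesitis, stated power 69%. H8: 56% vs 32%, 11% with Baseline dactylitis, stated power 66%. H9: stated power 76%. PA0010 arms: 420 BKZ and 280 placebo. Alpha 0.05 two-sided, with the power method a continuity-corrected chi-square (Section 2.4.2).

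**2. Reproducing the stated powers.** The SAP does not give the size of PA0011, so the powers can only be shown to be consistent. Assume 390 subjects in PA0011 at 2:1. The pooled arms are then 680 and 410, and the subgroups are 170 and 102.5 (25%) for H7 and 74.8 and 45.1 (11%) for H8.

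With s = 1/n1 + 1/n2 and p̄ the pooled rate, z = [|p1−p2| − s/2 − 1.96·√(p̄(1−p̄)s)] / √(p1(1−p1)/n1 + p2(1−p2)/n2), and power = Φ(z).

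- H7: (0.16 − 0.0078 − 0.1225)/0.0615 = 0.48, giving 68.5% (stated 69%).
- H8: (0.24 − 0.0178 − 0.1844)/0.0901 = 0.42, giving 66.3% (stated 66%).

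Both stay within 2 points of the stated figures for a PA0011 of roughly 360 to 425 at 2:1. No error is shown. Without the s/2 correction the same sizes give about 73% for each test.

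**3. What the sequence implies.** If the tests were independent and all earlier ones succeeded, the stated powers give 0.69 × 0.66 = 46% for passing H7 and H8, and 0.69 × 0.66 × 0.76 = 35% for passing H9 as well.

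**4. Effect of adding the Baseline score.** Logistic Wald tests were simulated with 8,000 trials per setting, on 170 vs 102 subjects (H7) and 75 vs 45 (H8). The models held treatment alone, or treatment plus the Baseline score, and the marginal response rates were kept at the SAP's values. Assumed, because the SAP gives nothing: LEI scores 1 to 6 with weights 0.30, 0.28, 0.15, 0.15, 0.06, 0.06; a normally distributed log LDI; and the prognostic strength, varied as the odds ratio per SD of the score.

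| Odds ratio per SD | H7 without | H7 with | H8 without | H8 with |
|---|---|---|---|---|
| 1.0 | 73.1% | 72.7% | 73.7% | 73.3% |
| 1.5 | 73.1% | 74.5% | 74.0% | 74.8% |
| 2.0 | 72.8% | 77.1% | 73.8% | 77.6% |
| 3.0 | 73.5% | 81.1% | 74.0% | 81.7% |

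A second set of runs (170 vs 103 and 75 vs 45) gave the same pattern, with gains at 3.0 of 8.9 points (73.0% to 81.9%) for H7 and 8.1 points (73.5% to 81.6%) for H8.

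**5. Passing both, if independent.** Without the score: 0.728 × 0.738 = 54%. With it: 0.771 × 0.776 = 60% at an odds ratio of 2.0, and 0.811 × 0.817 = 66% at 3.0.

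**The case against.** The planned model is a valid test of an odds ratio of 1. It is applied uniformly to the binary endpoints, and no part of the SAP contradicts it. A reader might infer from the unmodelled starting score that the comparison is biased, or that chance imbalance invalidates it. Neither follows in a randomised comparison: the type I error is intact, and only precision is lost. This part of the objection stands.

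A reader might also infer a large gain by applying the variance factor 1−ρ² to the stated powers. At ρ = 0.5, H7 gives (1.96 + 0.496)/√0.75 = 2.84, and Φ(2.84 − 1.96) = 81%. The documents do not support that figure. It starts from a continuity-corrected chi-square, whereas the planned Wald test already has about 73-74% at the assumed sizes. It also needs strong prognosis: for a normal covariate at these response rates, ρ = 0.5 is an odds ratio of about 4 per SD. The same rule gives only 69.4% and 66.4% at ρ = 0.1, and 70.8% and 67.8% at ρ = 0.2. Non-responder imputation, which scores dropouts and missing data as failures whatever the starting score, probably weakens the association further.

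Timing is the most serious practical objection. Treatment codes are released to an unblinded team at the Week 24 analysis (Section 4.3.1), and Amendment 3 was written for the Week 52 shells (Section 13.3). No dates are shown, but the codes may already have been released. Changing a confirmatory model after that would be worse than the omission. The PA0011 plan is not shown either, so an edit here may not be enough. Both points stand and shape the fix.

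What survives is that the trade is favourable: at most about one point lost if the score is not prognostic, and several gained if it is.

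**Conclusion.** The point holds as an efficiency weakness. Baseline LEI and LDI are in hand for every analysed subject and are unused in the two lowest-powered confirmatory tests, which gate H9. The change in power per test is 0 to -1 point at an odds ratio per SD of 1.0, +1 to 2 at 1.5, about +4 at 2.0 and +8 to 9 at 3.0. These figures rest on an assumed PA0011 size and assumed Baseline distributions. The joint figures also assume independence, which is doubtful for two endpoints drawn from the same pooled trials. Where the true value lies in this range cannot be told from the SAP, and at 1.5 or below the benefit is negligible.

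**What to change.** In Sections 8.2.2 and 4.1, pre-specify the H7 model as treatment, region, study-id and Baseline LEI, and the H8 model as treatment, region, study-id and Baseline LDI, for example log-transformed. Fix the functional form in advance. Leave non-responder imputation and the Wald test unchanged, report the already planned response-rate difference beside the odds ratio, and use the same model in any matching PA0011 pooled analysis.

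Make this the confirmatory model only if it is fixed before the Week 24 treatment codes are released. Otherwise keep the present test as confirmatory and add the adjusted model as a labelled supportive analysis.

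The cost is a sentence in each section, plus alignment with PA0011. The small downside is that the odds ratio becomes conditional on the Baseline score and will usually lie further from 1. The null value of 1 is unaffected, and the SAP already targets a conditional odds ratio.

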8.2.3 Supportive analyses of the secondary efficacy variables

As mentioned in [Table 4–2](#), the supportive analyses for all secondary variables will be performed using the modified composite estimand for binary variables (using MI-MCMC/monotone regression as in [Section 8.1.4.3](#)), the hypothetical estimand for continuous variables (using MI-MCMC/monotone regression as in [Section 8.1.4.4](#)) and OC.

For PASI90, the MI will be run on the PASI score on subjects involving at least 3% of BSA at Baseline.

For the MDA (and VLDA) MI analysis, subjects with BSA <3 at Baseline will always meet the criteria PASI ≤ 1 or BSA ≤ 3 except in the cases where a BSA score ≥ 3 is observed. Subjects involving at least 3% of BSA at Baseline will have their BSA values imputed using MI when deriving MDA (VLDA).

For enthesitis and dactylitis free-state based on the pooled data of PA0010 and PA0011 subjects (in the BKZ160mg Q4W and the Placebo group), the MI will be performed on the pooled dataset (using data from Baseline, Week 4, 8, 12 and 16) the same way as described in [Section 4.2.2.2](#):

- with the following covariates in that order for each SAS® PROC MI: region (North America, Western Europe and Eastern Europe) and study-id (“1” for PA0011 and “0” for PA0010)
- For MI on LDI : on subjects with LDI>0 at Baseline
- For MI on LEI : on all subjects (but the results will be reported for subjects with LEI>0 at Baseline).

In addition, subgroup analyses will be performed on the PASI90 response at Week 16 (in subjects with PSO involving at least 3% of BSA at Baseline) (Refer to [Section 4.8](#) for the list of subgroups of interest). The same analysis method used for the subgroup analysis of the primary endpoint will be performed, and the results will be presented similarly.

Enthesitis and dactylitis free state will be analyzed as supportive analyses in the PA0010 data only (successively using the NRI, the modified composite estimand and the OC strategies).

To assess the impact of the COVID-19 pandemic, the analysis of secondary efficacy endpoints included in the hierarchy will be repeated on the COVID-19-Free Set (on subjects from the Radiographic Set included in the COVID-19-Free-Set for the analysis of VdHmTSS) using the primary analysis method.

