The norm-based T-scores for the 2 SF-36 component summary (PCS and MCS) and the 8 domains are standardized with a mean of 50 and a standard deviation (SD) of 10 in the general US population (Maruish, 2011). An individual respondent's score that falls outside the T-score range of 45 to 55 should be considered outside the average range for the US general population. When considering group-level data, a score below 47 should be considered indicative of impaired functioning within that health domain or dimension. Similar to individual respondent

data, group mean scores of 47 or greater should be considered average or above average as compared to the general US population. Higher scores indicate a better health status.

For the calculation of the SF-36 norm-based T-scores for the 8 domains and the PCS and MCS, the scoring software Optum's PRO CoRE (version 1.4) will be used. The software uses updated 2009 U.S. population norms and applies a Full Missing Score Estimation method as follows:

- A health domain score (except the Physical Functioning domain) will be estimated provided that at least 1 non-missing response is available within that domain.
- For the Physical Functioning domain, item response theory will be used to develop a model for estimates of the missing score.
- Regression methods will then be applied to estimate the PCS and MCS on the basis of the available domains.

Change from Baseline at Week 16 in SF-36 PCS score is the 4th endpoint in the sequential testing hierarchy ([Table 4-5](#)).

8.2.1.4 MDA at Week 16

MDA is a state of disease activity deemed a useful target of treatment by both the subject and physician, given current treatment possibilities and limitations. The criteria that need to be met are based on key outcome measures in PsA and are shown below:

- Tender joint count ≤ 1
- Swollen joint count ≤ 1
- PASI ≤ 1 (for subjects with PSO involving at least 3% of BSA at Baseline) or BSA ≤ 3
- PtAAP (VAS) ≤ 15 mm
- PGA-PsA (VAS) ≤ 20 mm
- HAQ-DI ≤ 0.5
- Tender enthesial points ≤ 1 (LEI ≤ 1).

A subject has achieved MDA if 5 or more of the 7 above criteria are fulfilled.

The enthesitis instrument of the study (ie: LEI) will be used to determine whether a subject has ≤ 1 tender enthesial point.

The following rule will be applied for subjects with BSA < 3 at Baseline: Subjects with BSA < 3 at Baseline will always meet the criteria PASI ≤ 1 or BSA ≤ 3 except in the cases where a BSA score > 3 is observed.

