MDA at Week 16 is the 5th endpoint in the sequential testing hierarchy ([Table 4-5](#)).

8.2.1.5 Van der Heijde modified Total Sharp Score (vdHmTSS): Change from Baseline at Week 16

The degree of joint damage is to be assessed using the vdHmTSS as used in the evaluation of PsA (Van der Heijde et al, 2005). This methodology quantifies the extent of joint erosions (52 joints) and joint space narrowing (52 joints), with higher scores representing greater damage.

Radiographs of the hands and feet are to be taken using standardized imaging methodology, which is defined in the Hand and Foot Radiography Manual that will be provided as part of the Study Manual.

All enrolled subjects are required to have radiographs taken of both hands and both feet (a single posteroanterior view of each hand and a single dorsoplantar of each foot). Radiographs are to be read centrally and independently by 2 experienced readers. If the 2 primary readers disagree, adjudication will be performed by a third reviewer. Readers will be blind to treatment assignment and time course of the films. Additional details on radiograph reading, assessment, and adjudication should be given in the imaging charter.

The scoring methodology is outlined below.

Scoring of Erosions:

Bone erosions in the hands and feet will be scored in the following locations according to the following grading scheme:

Erosion Scoring Locations:

- 20 locations in each hand and wrist (left and right): 40 locations overall:
 - 4 Distal inter-phalangeal joints (2-5)
 - 4 Proximal Inter-Phalangeal Joints (2-5)
 - 5 Metacarpo-Phalangeal Joints (1-5)
 - Inter-Phalangeal Joint of the thumb
 - Proximal first Metacarpal Bone
 - Radius Bone
 - Ulnar Bone
 - Trapezium and Trapezoid (as one unit; multangular)
 - Navicular Bone
 - Lunate Bone.
- 6 joints in each foot (left and right), 12 locations overall for the 2 feet:
 - 5 Metatarso-phalangeal joints (1-5)
 - Inter-phalangeal joint of the first toe.

Erosion Grading Scheme:

- Scores will be based on the number and size of discrete erosions in each location as follows:
 - 0=Normal (no erosion)
 - 1=Discrete small erosion
 - 2=Either 2 discrete erosions or 1 larger erosion that do not cross the joint middle line

- 3=Combination of the above or 1 large erosion that cross the joint middle line of the bone
- 4=Combination of above adding up to 4
- 5=Combination of above adding up to 5 or more.

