8.3.1.9 Very Low disease activity (VLDA) response

Like MDA, VLDA is a state of disease activity deemed a useful target of treatment by both the subject and physician, given current treatment possibilities and limitations.

A subject is considered as having VLDA if all 7 of the criteria used for MDA and listed in [Section 8.2.1.4](#) are fulfilled.

If any of the 7 MDA criteria is not met, then the subject will be considered as non-responder.

VLDA response will be analyzed at Week 4, 8, 12, 16, 20, 24, 36, 52.

8.3.1.10 Proportion of Subjects with an IGA score of 0 (clear) or 1 (almost clear) AND at least a 2-grade reduction from Baseline in the subset of subjects with psoriatic skin lesions at Baseline

Method for derivation of this variable can be found in [Section 8.2.1.10](#).

The proportion of subjects with an IGA score of 0 (clear) or 1 (almost clear) AND at least a 2-grade reduction from Baseline in the subset of subjects with psoriatic skin lesions at Baseline will be analyzed at Week 4, 8, 12, 16, 20, 24, 36, 52.

For some subjects with BSA $\geq 3\%$ at Baseline, IGA data have not been captured at some post-Baseline visits when BSA $< 3\%$ at those visits. To address that, an additional supportive analysis will be performed in which these subjects will be considered as IGA responders at the respective visit.

In the context of this analysis, observed data for % of BSA affected by PSO will be also analyzed by visit using descriptive statistics.

8.3.1.11 Disease Activity Index for Psoriatic Arthritis (DAPSA) score, state and change from Baseline in DAPSA score

Disease Activity Index for Psoriatic Arthritis (DAPSA) is a composite score of patient global and pain VAS, TJC, SJC and hs-CRP (mg/L) that incorporates a pattern of peripheral arthritis that often is encountered in PsA. DAPSA score will be calculated as follows:

$$DAPSA = SJC + TJC + PGA-Arthritis + PtAAP + hs-CRP$$

where:

- SJC range from 0 to 66
- TJC ranges from 0 to 68
- PGA-Arthritis represents the patient's global assessment of arthritis ranging from 0 to 10 ; 0=best, 10=worst (using the unrounded VAS value that ranges from 0 to 100 mm and dividing this value by 10) ([Section 8.3.1.28](#))
- PtAAP ranging from 0 to 10, 0=best, 10=worst, (unrounded, by dividing the original value by 10)
- hs-CRP in mg/L (no upper limit applied).

DAPSA values will be categorized in the following disease activity states:

- Remission (REM) (DAPSA≤4)
- Low Disease Activity (LDA) (DAPSA >4 and ≤14)

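### For subjects with Baseline BSA below 3, the MDA skin-criterion exception is BSA >3 in SAP 8.2.1.4 but BSA ≥3 in the supportive MI analysis of 8.2.3

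*SAP*

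**What the plan says.** - **MDA (SAP 8.2.1.4).** "A subject has achieved MDA if 5 or more of the 7 above criteria are fulfilled". One of the seven is the skin criterion: PASI ≤1 (for subjects with at least 3% BSA at Baseline) or BSA ≤3. The section places the endpoint in the hierarchy: "MDA at Week 16 is the 5th endpoint in the sequential testing hierarchy".
- **Special rule, primary derivation (SAP 8.2.1.4).** The sentence beginning "The following rule will be applied for subjects with BSA" covers only subjects below 3 at Baseline. They always meet the skin criterion "except in the cases where a BSA score" **above 3** is observed.
- **Special rule, MI analysis (SAP 8.2.3).** The sentence beginning "For the MDA (and VLDA) MI analysis, subjects with BSA" repeats the rule for the same subjects and the same criterion, but the exception applies when a BSA of **3 or more** is observed. Subjects at 3% or more at Baseline are outside this rule; their BSA is imputed instead.
- **VLDA (SAP 8.3.1.9).** "A subject is considered as having VLDA if all 7 of the criteria used for MDA". The skin criterion therefore carries over to VLDA unchanged.

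**The concern.** The supportive MI analysis of MDA uses the modified composite estimand. It should differ from the primary analysis only in which discontinuations count as intercurrent events and in how missing data are handled. If the skin criterion also has a different boundary, a subject with complete data and no intercurrent event can be classified differently in the two analyses. Part of any gap between them would then come from the endpoint definition rather than from the missing-data assumption.

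VLDA has no primary analysis to fall back on. Under 4.2.1.5 and Table 4-2, its non-responder and MI results have no designated priority, so two results of equal standing would use different definitions. MDA and VLDA are also reported at Weeks 4, 8, 12, 16, 20, 24, 36 and 52 (8.3.1.8, 8.3.1.9), so the mismatch could recur at each of these visits.

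**Working it through.** No power, sample-size or alpha figure depends on this point, so the check compares the two rules directly.

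**Step 1: skin criterion for a subject with Baseline BSA below 3, exception read as criterion not met.**

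| Observed BSA | BSA ≤3 itself | 8.2.1.4 (exception >3) | 8.2.3 (exception ≥3) |
|---|---|---|---|
| 0, 1, 2, 2.9 | met | met | met |
| 3 | met | met | **not met** |
| 3.1, 4 | not met | not met | not met |

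The rules differ only at exactly 3. At that value 8.2.1.4 agrees with the criterion and 8.2.3 does not. PASI gives no alternative route, because 8.2.1.4 ties the PASI part to subjects with at least 3% BSA at Baseline.

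**Step 2: effect on response at an observed BSA of exactly 3.** Let k be the number of the other six criteria that are met.

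- MDA requires 5 of 7. Under 8.2.1.4 the count is k + 1; under 8.2.3 it is k. The two give different answers only when k + 1 ≥ 5 and k < 5, that is k = 4 (5 of 7, responder, against 4 of 7, non-responder).
- VLDA requires 7 of 7. The answers differ only when k = 6 (7 of 7 against 6 of 7).

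**Step 3: consistency within the MI analysis.** A subject at 3% or more at Baseline whose BSA is 3 at the visit satisfies BSA ≤3. A subject who began below 3 and has the same value would not. The SAP gives no reason for this difference.

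**Step 4: size.** The planned BKZ and placebo arms are 420 and 280 (2.3.1), and 2.4.2 assumes 60% of subjects have BSA ≥3%. The rule therefore applies to about (420 + 280) × 0.40 = 280 subjects under the planning assumption. The SAP does not say how many of them would be observed at exactly 3, or how many of those would meet exactly 4 of the other 6 criteria, so no count can be derived. Each MDA reclassification would move an arm's proportion by 1/420 = 0.24 percentage points (BKZ) or 1/280 = 0.36 percentage points (placebo), always downwards in the MI analysis.

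**The case against.** The strongest reply is that neither section says the subject fails at the cut-off. The exception may only withdraw the automatic pass, after which the criterion is judged on the observed value. A BSA of 3 satisfies BSA ≤3, so both sections would classify the subject alike and no one would change status. That reading is possible, and it makes the reclassification conditional on how the sentence is programmed. It does not remove the inconsistency: the ≥3 threshold would then have no effect at exactly 3, and the two sections would still state different rules.

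A second reply is that the intended symbol is uncertain. The Amendment 2 log (13.2, Change #17), where the 8.2.3 sentence was added, prints >3. It also prints strict signs where the current section has ≤, so it cannot settle the matter. Change #15 in the same log records that 8.2.1.4 was moved from ≥3 to >3. This is useful only as evidence of intent; the conflict is between two current sections.

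A reader might infer that the MDA skin criterion has two cut-offs for everyone, or that the confirmatory result is at risk. The documents support neither. The rule is confined to Baseline BSA below 3, and the primary analysis of H5 uses the 8.2.1.4 derivation with non-responder imputation (8.2.2, Table 4-2). Nor does every subject observed at exactly 3 change VLDA status; that requires all six other criteria to be met.

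**Conclusion.** The inconsistency is real and minor. The ≥3 exception in 8.2.3 conflicts with 8.2.1.4 and with the criterion it is meant to implement. Applied literally, it reclassifies only subjects with Baseline BSA below 3, an observed BSA of exactly 3, and exactly 4 of the other 6 criteria met (MDA) or all 6 met (VLDA). It affects the supportive MI analysis of MDA and the MI summaries of VLDA, and leaves the primary H5 test unchanged. That so few subjects are likely to be affected is a judgement from how narrow these conditions are, not a figure from the SAP. If reclassified subjects fall in both arms, their effect on the treatment difference partly cancels.

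**What to change.** In 8.2.3, change the exception for subjects with Baseline BSA below 3 from a BSA of ≥3 to a BSA of >3, so that it matches 8.2.1.4 and the criterion BSA ≤3. It would help to state in both sections that an observed BSA above 3 means the skin criterion is not met, which closes off the alternative reading. The cost is one symbol and a short clause in the SAP, plus a check of the MDA and VLDA derivation code. The primary analysis does not change.
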